## 10.4.1.2 Secondary Efficacy Endpoints

All secondary analyses will be based on the FAS population. As appropriate, continuous secondary endpoints will be analyzed using mixed model repeated measures (MMRM) with a random effect for participant and fixed effects for treatment, visit, treatment-by-visit interaction, and baseline stratification factors. The baseline value of the endpoint being tested will be added into the model as a covariate. In addition, as appropriate analysis of covariance models will be used to analyze continuous secondary endpoints with treatment and factors used for randomization as fixed effects. The baseline value will be added into the model as a covariate.

Cochran-Mantel-Haenszel tests will be used to compare dichotomous endpoints between either BMS-986278 dose group vs placebo.

The Kaplan-Meier product limit method will be used to estimate the survival curves for time-to-event endpoints. Treatment comparisons between each BMS-986278 dose group and placebo will be performed using the log-rank test stratified by baseline stratification factors.

The PF-ILD cohort will be analyzed separately from the primary study cohort of IPF. The PF-ILD statistical analysis methods will be similar to IPF cohort. The details will be described in the SAP.

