Height and weight measurement	X	X					X			X		Height measured at screening only.
Laboratory/Saf	ety Assessm	ents										
12-lead ECG	X	X			X		X			X		All ECGs must be performed prior to bronchodilator administration OR at least 20 hours after bronchodilator administration. ECG on Day 1, Weeks 4 and 12 to be collected before morning dosing.  See Section 9.4.3 for further details.
Serial ECG for participants enrolled in intensive PK substudy			See notes.									Intensive PK substudy only. According to schedule in Table 7.
Clinical laboratory samples	X	X		X	X	X	X	X	X	X	X	Hematology, chemistry, and urinalysis.
Physical examination	X	X			X		X			X	X	
Vital signs for all participants	X	x d	X	X	X	X	X	X	X	X	X	Predose vital signs include body temperature, respiration rate, and orthostatic BP and HR.  Refer to Section 9.4.2 for further details on vital signs.

Protocol Amendment No.: 05

Table 1: Schedule of Activities for Study IM027040 (Main Study)

					Treati	ment (Da	y 1 to W	eek 26) a			Post-	
	Screening			Day 8	Day 29	Day 57	Day 85	Day 113	Day 141	Day 183	treatment	
	(Day -42 to Day -1)	Day 1	Day 2 b	Week 1 (± 3 days)	Week 4 (± 3 days)	Week 8 (± 5 days)	Week 12 (± 5 days)	Week 16 (± 5 days)	Week 20 (± 5 days)	Week 26 (+ 5 days)	follow-up c (28 ± 7 days after Week 26)	Notes
												During post-Day 1 visits, additional BP monitoring is required (similar to Day 2 visit) if either asymptomatic or symptomatic low BP criteria are met, as specified in Section 5.1.2.1.
Orthostatic evaluations				At every visit, including screening, symptoms that could indicate the presence of orthostatic intolerance, orthostatic hypotension, and orthostatic tachycardia will be gathered.  Refer to section 9.4.2 and section 5.1.2.1 further details on orthostatic evaluations.								
Serial BP and HR for participants enrolled in intensive PK substudy			See notes.									Intensive PK substudy only. According to schedule in Table 7.
Pharmacokinet	ic and Biom	arker	nrker Assessments									
Blood samples for sparse PK profiling			See notes.									According to schedule in Table 6.
Blood samples for intensive PK profiling						See	notes.					Intensive PK substudy only. According to schedule in Table 7.

930149229 6.0

Protocol Amendment No.: 05

Date: 22-Sep-2022

Approved vb.0

Table 1: Schedule of Activities for Study IM027040 (Main Study)

					Treati	ment (Da	y 1 to W	eek 26) a			Post-	

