#### Spirometry Parameters and Calculation of Predicted Values:

The following parameters will be measured as part of the spirometry assessment:

- FEV1 (mL) and percent predicted forced expiratory volume in 1 second (ppFEV1)
- FVC (mL) and ppFVC
- FEV1/FVC ratio

The 2012 Global Lung Function Initiative Equations' will be used to estimate ppFVC (Quanjer, et al.).

Additional details on the FVC assessment and ppFVC calculation are in the Study Manual.

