#### IPF and PF-ILD cohorts:

- Proportion of participants with a at least 10% absolute decline from baseline in ppFVC (%) at Weeks 4, 8, 12, 16, 20, and 26
- Proportion of participants with > 0% change in ppFVC at Weeks 4, 8, 12, 16, 20, and 26
- Time to first acute exacerbation
- Time to first occurrence ≥ 10% absolute decline in ppFVC (%)
- Absolute change in ppFVC (%) from baseline to Week 26
- Absolute change in FVC (mL) from baseline to Week 26
- Absolute change in DLCO SB (mL/min/mmHg) (corrected for hemoglobin) from baseline to Week 26
- Absolute change in ppDLCO SB (%) (corrected for hemoglobin) from baseline to Week 26
- Change in walking endurance/distance from baseline at Week 26 as measured using the 6MWT
- Proportion of participants with acute exacerbations (evidence of which will be captured in the eCRF) of lung fibrosis defined as an acute, clinically significant, respiratory deterioration characterized by evidence of new widespread alveolar abnormality, as follows:
  - 1. Acute worsening or development of dyspnea (< 1 month duration)
  - 2. Imaging with new bilateral ground-glass opacity and/or consolidation superimposed on a background pattern consistent with fibrotic lung disease.
  - 3. Respiratory deterioration not fully explained by cardiac failure of fluid overload

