#### 10.4 Statistical Analyses

The Statistical Analysis Plan (SAP) will be developed and finalized before first unblinding event of the study (see Section 10.4.5), and will provide detailed specifications of the analysis of all efficacy endpoints and safety data. This section provides a summary of planned statistical analyses.

Categorical data will be summarized using counts and percentages. Continuous data will be summarized using n, mean, standard deviation, median, minimum, and maximum unless otherwise specified.

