## 10.4.1 Efficacy Analyses

## 10.4.1.1 Primary Efficacy Endpoint

The primary endpoint is the rate of change in ppFVC in IPF participants (estimated from measurements taken over 26 weeks of treatment). The decrease in ppFVC is assumed to be linear within each participant over the 26 weeks.

The primary analysis will compare the rate of change in ppFVC from baseline to Week 26 using a random coefficient linear mixed model using the Full Analysis Set (FAS). The model will include ppFVC at each visit as dependent variable, random coefficients for intercept and slope and fixed effect terms for treatment, time since randomization, treatment × time interaction, and baseline stratification factors. No imputation of missing values will be performed for the primary analysis. Sensitivity analysis may be performed to assess the impact of missing values as well as impact of dose reduction on the primary analysis. There will be no adjustment for multiple comparisons.

Subgroup analyses will be performed for concomitant use of pirfenidone or nintedanib therapy (vs neither pirfenidone nor nintedanib) for IPF and for other demographic and baseline characteristics.

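### The secondary MMRM names a participant random effect as its only within-participant term; fitted that way, Week 26 ppFVC intervals would generally be too narrow, by an amount the documents do not fix

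*Combined protocol and SAP*

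**What the plan says.** Protocol Section 10.4.1.2 analyses continuous secondary endpoints with a "mixed model repeated measures (MMRM) with a random effect for participant and fixed effects for treatment, visit, treatment-by-visit interaction", plus stratification factors and the baseline value. The participant random effect is the only within-participant term named. No residual covariance, robust standard error or degrees-of-freedom method is given there or elsewhere in the text reviewed.

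The same section adds a second method: "In addition, as appropriate analysis of covariance models will be used to analyze continuous secondary endpoints". Both methods are conditional on being suitable, and neither is named as the lead.

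Section 10.4.1.1 models ppFVC differently for the primary analysis, with "random coefficients for intercept and slope and fixed effect terms for treatment, time since randomization" among its terms, and takes each participant's course as linear over 26 weeks. It also says: "There will be no adjustment for multiple comparisons".

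Section 10.3.2 lists "Absolute change in ppFVC (%) from baseline to Week 26" as a secondary endpoint for both cohorts. Section 10.4 presents itself as a summary and leaves detail to a SAP that "will provide detailed specifications of the analysis of all efficacy endpoints and safety data" and is to be final before the first unblinding.

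**The concern.** The plan holds two views of the variance of one outcome in the same participants. If slopes differ between participants, as the primary model allows, participants spread apart and change from baseline is most variable at Week 26. A random intercept with independent, equal-variance residuals does not allow this. It uses one variance pooled over six visits, and so bases the Week 26 standard error on an average that is usually too small for that visit.

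At stake are the nominal 95% intervals and p-values for Week 26 change in ppFVC. Change in FVC (mL) comes in by inference only. Section 9.1.1 says that reference equations "will be used to estimate ppFVC", and Table 1 notes "Height measured at screening only". The predicted value should therefore hardly move within a participant over 26 weeks, and the two measures should change nearly in proportion.

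**Working it through.** **Inputs from the documents.** Difference 2.5 ppFVC points, SD 6.5, two-sided 0.05 per dose, 80 per arm, 80% completion (Section 10.1); spirometry at Weeks 4, 8, 12, 16, 20 and 26 (Table 1).

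**Assumptions.** The slope variance is not given. Let f be the share of Week 26 change variance due to slopes, varied from 0 to 0.75. Intercept and slope are uncorrelated, except in step 4.

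**1. Table 10 reproduced.** Half-width = 1.96 × 6.5 × √(2/n). At n = 80 this is 2.01, giving 0.49 to 4.51. At n = 60 and 100 it gives 0.17 to 4.83 and 0.70 to 4.30. All three match, so 6.5 acts as the per-participant SD.

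**2. Variance ratio.** With t as a fraction of 26 weeks, the variance of change is 6.5² × (1 − f + f·t²), which equals 6.5² at Week 26. With complete data, the Week 26 contrast is the difference in Week 26 means. The model as written attaches to it the variance averaged over six visits.

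- m = mean of t² = (16 + 64 + 144 + 256 + 400 + 676) / (6 × 676) = 0.384
- model variance / true variance = 1 − f(1 − m) = 1 − 0.616f
- actual error = 2 × [1 − Φ(1.96 × √ratio)]

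**3. Results, complete data, 80 per arm, observed difference 2.5.** Slope SD is 6.5√f.

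| f | Slope SD (points per 26 weeks) | SE ratio | Actual error | Interval from the model as written |
|---|---|---|---|---|
| 0 | 0 | 1.00 | 5.0% | 0.49 to 4.51 |
| 0.10 | 2.06 | 0.97 | 5.8% | 0.55 to 4.45 |
| 0.25 | 3.25 | 0.92 | 7.1% | 0.65 to 4.35 |
| 0.50 | 4.60 | 0.83 | 10.3% | 0.82 to 4.18 |
| 0.75 | 5.63 | 0.73 | 15.1% | 1.02 to 3.98 |

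A REML simulation of the random-intercept model, with 80 per arm and 20% random dropout, gave coverage of 95.1%, 93.1%, 88.9% and 82.8% at f = 0, 0.25, 0.50 and 0.75. Dropout therefore does not remove the effect.

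**4. Direction.** The SE ratio was computed with baseline adjustment over a grid of assumed values: intercept SD 12 and 18, reading-error SD 2 to 4, slope SD 2 to 6, intercept-slope correlation −0.9 to 0.9. It was below 1 in all but three cells, which gave 1.006, 1.007 and 1.016. All three had correlation −0.9 and slope SD 2.

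**5. Alternatives.** In a second simulation (40 and 80 per arm, with and without 20% dropout, f from 0 to 0.75), an unstructured covariance with Kenward-Roger adjustment kept error between 4.4% and 5.7%. The Week 26 ANCOVA kept it between 4.4% and 6.1%. The unstructured fits started from the true covariance, so their convergence says little about real data.

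**6. PF-ILD, 40 per arm.** Section 10.1 used no statistical considerations for this cohort, so 2.5 and 6.5 are borrowed from IPF.

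- n = 40: correct half-width 2.85, interval −0.35 to 5.35. The model as written excludes zero once f exceeds [1 − (2.5/2.849)²]/0.616 = 0.37.
- n = 32 (80% of 40): correct half-width 1.96 × 6.5 × √(2/32) = 3.185, interval −0.68 to 5.68. The threshold is [1 − (2.5/3.185)²]/0.616 = 0.62.

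A likelihood fit that uses partial data would fall between the two.

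**The case against.** The strongest reply is that the model criticised is not fully in the text. Section 10.4.1.2 never says that residuals are independent with equal variance, Section 10.4 defers detail to the SAP, and many statisticians read MMRM as implying an unstructured covariance. A reader should therefore not infer that the plan commits to a miscalibrated analysis; the SAP can settle the matter. What remains is that the protocol does more than stay silent. It names one within-participant term, and a SAP that follows the wording would inherit the problem. If an unstructured covariance is meant, the participant random effect is redundant and the sentence still needs changing.

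Two stronger readings are tempting. The first is that intervals are too narrow whenever slopes vary. Step 4 shows that this is not universal. The second is that a PF-ILD conclusion would change. That rests on a borrowed difference and SD, and the threshold moves from 0.37 to 0.62 with the number of completers. Section 10.4.4 does describe PF-ILD results through effect sizes and confidence intervals, but it names neither the MMRM nor Week 26 change.

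It is also fair that f is unknown and that small values do little harm: 5.8% at f = 0.10.

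**Conclusion.** The point holds conditionally. Fitted as written, the secondary MMRM conflicts with the random slopes of the primary model, and Week 26 intervals for change in ppFVC would generally be too narrow. Actual error runs from 5.0% at f = 0 to 15.1% at f = 0.75, given complete data and uncorrelated intercept and slope. The documents do not say where in that range the trial lies. The extension to FVC (mL) is an inference. The six-visit figures do not apply to DLCO or the 6MWT, which have two post-baseline visits.

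The reach is limited. The primary slope analysis and the Week 26 ANCOVA are unaffected, no multiplicity-controlled claim depends on the MMRM, and Section 10.1 treats PF-ILD as supportive. In Table 10's 80-per-arm case zero is excluded under either model. No firm claim about a changed PF-ILD conclusion is supported.

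**What to change.** In Section 10.4.1.2, or in the SAP before the first unblinding:

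- Replace the participant random effect with an unstructured within-participant covariance across the scheduled visits, with Kenward-Roger degrees of freedom.
- Name one fallback structure for non-convergence that still lets the variance differ by visit, for example heterogeneous Toeplitz.
- State whether the MMRM or the ANCOVA is the lead Week 26 analysis.

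The cost is a sentence or two of text and more covariance parameters: 6 × 7 / 2 = 21 for six-visit spirometry, and 2 × 3 / 2 = 3 for DLCO and the 6MWT. Intervals become somewhat wider but correctly calibrated. On Table 10's inputs the half-width at 80 per arm is 2.01, against 1.85 at f = 0.25 or 1.68 at f = 0.50 under the model as written.

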## 10.4.2 Pharmacokinetic Analyses

The PK population will be defined as all randomized participants who receive at least 1 administration of BMS-986278 and have any quantifiable concentration data. PK analyses will be based on the PK population. BMS-986278 and BMT-323719 concentration data as well as nintedanib and pirfenidone concentration data from participants also receiving nintedanib or pirfenidone will be summarized by visit and timepoint, as applicable, using descriptive statistics for the PK population. Descriptive statistics will also be provided for the plasma BMS-986278 PK parameters for each BMS-986278 dose. In addition, trough concentrations of nintedanib and pirfenidone will be summarized by visit. For the participants that undergo intensive PK assessments, geometric means and percent coefficients of variation (%CV) will be presented for PK parameters such as AUC(0-8), Cmax, and Ctrough. Participants in the PET-tracer substudy will only have their PK concentration data listed and not summarized.

Medians and ranges will be presented for Tmax. Scatter plots for Ctrough over time will be presented for each active treatment to assess the attainment of steady state. Additionally, Ctrough will be summarized (geometric mean and %CV) by visit and active treatment. Results of these analyses will be reported separately.

Concentration data from both sparse and intensive PK samples will be used to further characterize the PK of BMS-986278 using population PK analysis, and to estimate model-based PK parameters such as apparent oral clearance at steady state (CLss/F) and apparent volume of distribution at steady state (Vss/F). Results of these analyses will be reported separately.

#### 10.4.3 Safety Analyses

Analyses of safety data will be based on the safety set, which is defined as all participants who take at least 1 dose of study treatment.

Treatment-emergent AEs and study drug-related AEs and SAEs will be summarized using counts and percentages of participants experiencing the event as well as the number of events by system organ class, preferred term, and treatment group. Physical examination findings, vital signs, clinical laboratory test results, and ECG test results will be summarized using descriptive statistics (n, mean, standard deviation, median, minimum, and maximum) for continuous variables and frequency distributions (counts and percentages) for categorical variables.

The proportions of participants in each treatment group who discontinue study treatment due to changes in BP will be summarized using descriptive statistics.

The PF-ILD cohort will be analyzed separately from the primary study cohort of IPF.

#### IM027040 LPA1 Antagonist

## 10.4.4 Other Analyses

PK and biomarker exploratory analyses will be described in the SAP and finalized before database lock. The population pharmacokinetics analysis and pharmacodynamic analyses will be presented separately from the main clinical study report. Exploratory analyses of COAs will be described in the SAP finalized before database lock.

Exploratory PK will be summarized by dose and timepoint for the PK population. If warranted, analysis of PK and exposure-response relationships will be reported separately from the clinical study report (CSR).

Selected biomarkers will be summarized by treatment and timepoint using the FAS population. Summaries will be provided for raw, change from baseline, and percent change from baseline.

At the time of database lock for the IPF cohort (Week 26 of the main study), the OTE for the IPF cohort will continue unblinded until completion. To better assess longer-term efficacy and safety with BMS-986278, select efficacy (eg, FVC) and safety data from the OTE portion of the IPF cohort will be reviewed by the sponsor based on the locked database. The blind will be maintained for the PF-ILD cohort until the database lock for the PF-ILD cohort (Week 26 of the main study).

An analysis is planned for the PF-ILD cohort when 100% of participants (N = 40/arm) complete Week 26. This analysis will be performed and results reviewed by the independent DMC. Results will be descriptive and based on estimation of effect size and associated confidence intervals. Further details on statistical considerations, review of data, and unblinding will be included in the DMC Charter and SAP. At the time of the PF-ILD cohort main study database lock (Week 26 of the main study), the OTE for the PF-ILD cohort will continue unblinded until completion.

All safety, tolerability, and efficacy data from the OTE will be analyzed separately from the main study. The presentation of participants treated with BMS-986278 during the OTE will be done by the following groups: participants randomized to 30 mg at the start of the main study, participants randomized to 60 mg at the start of the main study, participants randomized to 30 mg in the OTE (placebo participants in the main study), participants randomized to 60 mg in the OTE (placebo participants in the main study), participants who received an unblinded reduced dose of 10 mg at the start of the OTE.

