Table 3: Objectives and Endpoints

Objectives	Endpoint(s)		
To further evaluate the efficacy of BMS-986278 in participants with IPF or PF-ILD that participate in the OTE.	• FVC trajectory (eg, rate of change of ppFVC [%] and FVC [mL] from Week 26 in the main study to Week 26 in the OTE and from baseline in the main study to Week 26 in the OTE)		
	DLCO trajectory (eg, rate of change of ppDLCO SB [%] and DLCO SB [mL/min/mmHg] from Week 26 in the main study to Week 26 in the OTE and from baseline in the main study to Week 26 in the OTE)		
	
 
Changes in quantitative lung fibrosis using the Quantitative HRCT Fibrosis Score
 
		
	Changes in HRQoL as measured by the L-PF		
	
 
Changes in walking endurance/distance as measured using the 6MWT
 
		
	
 
Blood-based biomarkers of lung fibrosis and inflammation; including gene expression profiles
 
		
To assess the impact of SARS-CoV-2 serologic status on participants with IPF or PF-ILD receiving BMS-986278.	• Exploratory measurements of SARS-CoV-2 serology (anti-SARS-CoV-2 total or IgG) from serum samples collected at the end of the OTE.		

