#### 5 STUDY DESIGN

## 5.1 Overall Design

This is a Phase 2 randomized, double-blind, placebo-controlled clinical study investigating the efficacy and the safety and tolerability of BMS-986278 in participants with pulmonary fibrosis. In the primary cohort, a total of approximately 240 participants with IPF will be randomized to receive 30 mg or 60 mg BMS-986278 BID or placebo BID at a ratio of 1:1:1 for 26 weeks in the main study. Stable standard of care (SOC) background therapy for IPF with either nintedanib or pirfenidone will be allowed.

In a secondary cohort, a total of approximately 120 participants with PF-ILD will be randomized to receive 30 mg or 60 mg BMS-986278 BID or placebo BID at a ratio of 1:1:1 for 26 weeks. Participants with PF-ILD will be allowed to remain on stable background therapies commonly used as part of their usual care, including nintedanib, pirfenidone, and/or select immunosuppressive medications (ie, azathioprine, mycophenolate mofetil, mycophenolic acid, and/or tacrolimus).

Protocol Amendment No.: 05

IPF and PF-ILD participants receiving 30 mg or 60 mg (or placebo) BMS-986278 BID in the main study who meet low BP criteria may be dose reduced to 10 mg BMS-986278 BID (or placebo for 10 mg BID) (refer to Section 5.1.2.1).

An optional treatment extension (OTE) that will last 26 weeks will be offered to IPF and PF-ILD participants that complete the 26-week main study. All participants will receive active treatment in the OTE. Participants who received 30 mg placebo tablets in the main study will be randomized to receive 30 mg or 60 mg BMS-986278 BID, and participants who received 30 mg or 60 mg BMS-986278 BID in the main study will continue with the assigned doses. Participants receiving 30 mg or 60 mg BMS-986278 BID in the OTE will remain blinded to study treatment until the database lock for analyses of the 26-week main study in IPF and PF-ILD cohorts, respectively. At the time of main study database lock in each cohort, the OTE will be unblinded for that cohort. Participants who dose reduced and received 10 mg BMS-986278 BID or placebo for 10 mg BMS-986278 BID in the main study will receive 10 mg BMS-986278 BID unblinded in the OTE. Participants receiving 30 mg or 60 mg BMS-986278 BID in the OTE who meet low BP criteria may be dose reduced to 10 mg BMS-986278 BID (refer to Section 5.1.2.1).

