All participants in the OTE will receive active treatment with BMS-986278. Participants that receive 30 mg BMS-986278 in the main study will continue on 30 mg BMS-986278 in the OTE and remain blinded to dose. Participants that receive 60 mg BMS-986278 in the main study will continue on 60 mg BMS-986278 in the OTE and remain blinded to dose. Participants that receive 2 placebo tablets for 30 mg BMS-986278 in the main study will be randomized at a ratio of 1:1 to receive either 30 mg BMS-986278 or 60 mg BMS-986278 and will be blinded to dose in the OTE.

Participants that receive 10 mg BMS-986278 or placebo for 10 mg BMS-986278 in the main study will be assigned to receive 10 mg BMS-986278 and will be unblinded in the OTE.

Refer to Figure 3 for the OTE study design.

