#### Day 2 study visit:

On Day 2, participants will be issued new kits/containers. Participants will not self-administer the morning dose; the dose will be administered at the site.

At the Day 2 visit, participants will receive a reduced dose. Those randomized to 30 mg or 60 mg BMS-986278 will have their medication kits/containers replaced with 10 mg BMS-986278. Those randomized to placebo will have their medication kits/containers replaced with the placebo for 10 mg BMS-986278. These participants will continue on 10 mg BMS-986278 BID or matching placebo for 10 mg BMS-986278 BID. All instances of dose reduction are communicated by the site or vendor to the central study team.

On Day 2, participants will remain at the site for at least 4 hours post dose. Orthostatic BP and HR will be performed predose and 1.5, 2, and 4 hours post dose. Participants will be carefully monitored for symptoms associated with low BP.

If either *asymptomatic* or *symptomatic* low BP criteria are met (refer to Day 1 BP monitoring in Section 5.1.2.1 for details), participants will be discontinued from study treatment (but continue in the study). All other participants will remain on reduced dose (10 mg BMS-986278 BID) or matching placebo for 10 mg BMS-986278 BID).

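### Section 10.4.4 keeps former-placebo and former-active participants apart at 30 mg and 60 mg in the extension, but pools them at 10 mg

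*Combined protocol and SAP*

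**What the plan says.** Section 10.4.4 names five groups for presenting OTE data:

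- two by main-study randomization, the first being "participants randomized to 30 mg at the start of the main study", with a matching 60 mg group;
- two for former-placebo participants, the first being "participants randomized to 30 mg in the OTE (placebo participants in the main study"), again with a matching 60 mg group;
- one for 10 mg: "participants who received an unblinded reduced dose of 10 mg at the start of the OTE".

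Section 7.4 (Day 2 visit) sets out how a participant comes to the reduced dose in the main study. On the active arms, "Those randomized to 30 mg or 60 mg BMS-986278 will have their medication kits/containers replaced with 10 mg BMS-986278". On the placebo arm, "Those randomized to placebo will have their medication kits/containers replaced with the placebo for 10 mg BMS-986278". Section 7.2 then brings both together for the extension: "Participants that receive 10 mg BMS-986278 or placebo for 10 mg BMS-986278 in the main study will be assigned to receive 10 mg BMS-986278". By contrast, Section 5.1 states that "participants who received 30 mg or 60 mg BMS-986278 BID in the main study will continue with the assigned doses".

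Table 3 gives the exploratory FVC and DLCO trajectories in the OTE over two example windows: "Week 26 in the main study to Week 26 in the OTE and from baseline in the main study to Week 26" of the OTE.

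**The concern.** The plan separates prior placebo from prior active treatment at two doses and not at the third, and gives no reason for the difference. If the list is followed as written, two things in the 10 mg column become hard to interpret.

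- **Efficacy.** The trajectory from main-study baseline to OTE Week 26 averages people who took active drug in both periods with people who took placebo in the first.
- **Safety.** Former-placebo participants meet the drug for the first time on OTE Day 1. Former-active participants are restarting a dose they have already taken. Section 5.4.1 makes safety and tolerability a chief focus of the OTE, and Section 9.2.5 makes blood-pressure events adverse events of special interest, so the distinction bears on the events of most interest.

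Section 5.5 expects that 10 mg data may help describe exposure-efficacy and exposure-safety relationships. A column of mixed prior exposure serves that purpose poorly.

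**Working it through.** The plan states no figure on this point to reproduce. The check sets the grouping against the assignment rules and then counts scheduled exposure.

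**1. Who falls in each group**

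| OTE starting dose | Former active | Former placebo | Groups in Section 10.4.4 |
|---|---|---|---|
| 30 mg | yes | yes | 2, separate |
| 60 mg | yes | yes | 2, separate |
| 10 mg | yes (reduced from 30 or 60 mg) | yes (placebo for 10 mg) | 1, pooled |

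That makes five groups as listed, and six if 10 mg is treated like the other doses.

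**2. Scheduled time on placebo, per participant in the 10 mg column**

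Inputs: 26 treatment weeks in the main study and 26 in the OTE (Section 5.1), so 26 + 26 = 52.

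| Window (Table 3) | Former placebo | Former active |
|---|---|---|
| Main-study baseline to OTE Week 26 | 26/52 = 50% | 0/52 = 0% |
| Main-study Week 26 to OTE Week 26 | 0/26 = 0% | 0/26 = 0% |

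The 50% belongs to each former-placebo participant. It is not the placebo share of the pooled column.

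**3. What the pooled share would depend on**

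Let R be the ratio of the dose-reduction rate on active arms to that on placebo. With 1:1:1 allocation and equal OTE uptake, the former-placebo share of the 10 mg group is 1/(1 + 2R). The documents give neither R nor uptake, so the following is an illustration under assumed values only. The last column is the share multiplied by 26/52.

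| Assumed R | Former-placebo share of group | Placebo share of the group's 52-week scheduled time |
|---|---|---|
| 0.5 | 1/2 = 50% | 25% |
| 1 | 1/3 = 33% | 17% |
| 2 | 1/5 = 20% | 10% |
| 5 | 1/11 = 9% | 4.5% |
| 10 | 1/21 = 5% | 2.4% |

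**4. Length of the interruption before OTE dosing**

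Section 5.1.4 starts OTE treatment 1 to 15 days after the Week 26 visit, not after the last dose. Section 9.5.1 allows the Week 26 sample up to 5 days after the last dose. The longest gap on those figures is 5 + 15 = 20 days. Table 1 gives nearly the same: last dosing on Day 182, visit no later than Day 183 + 5 = Day 188, OTE start no later than Day 188 + 15 = Day 203, so 203 − 182 = 21 days elapsed, with 20 whole days between. Time off drug can therefore reach about 20 days within the stated windows. It can be longer where a window is extended under footnote a of Table 1.

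**The case against.** The strongest reply is that Section 10.4 describes itself as a summary and leaves detailed specifications to an SAP whose text is not in the supplied document, so the 10 mg group may yet be subdivided there. That is possible. But Section 10.4.4 already fixes the grouping, and an SAP that follows it would carry the pooling forward.

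The second reply is that the 10 mg column can never be read like the others. Its members are selected on low blood pressure, are not randomized to 10 mg, and know their dose from the start of the OTE. This stands. Even after a split, the former-active part would mix people reduced from 30 mg and from 60 mg at different visits. The split removes the mixing of placebo and active time and nothing more.

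The third reply is that little is at stake: OTE endpoints are exploratory, the two cohorts are analyzed separately, the subsets will be small, and main-study treatment is recorded, so nothing is lost for good. This also stands, and it sets the weight of the point.

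A reader might further infer that some participants are counted twice, since those randomized to 30 mg or 60 mg and later reduced literally fit both a continuation group and the 10 mg group. The documents do not support that as the intention. The same sentence lists 10 mg separately, and Sections 5.1 and 7.2 tie continuation to those receiving 30 mg or 60 mg. Only the wording needs tightening.

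**Conclusion.** The point holds as a minor one. As written, the 10 mg OTE column pools former-placebo with former-active participants, while the 30 mg and 60 mg columns do not. In the baseline-to-OTE-Week-26 window, each former-placebo member contributes 26 scheduled placebo weeks out of 52 and each former-active member none. The safety column mixes first exposure with re-exposure after a break of up to about 20 days from the last dose within the stated windows.

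Three stronger readings go beyond the documents:

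- that half of the 10 mg column's time is placebo time: the group-level share depends on reduction rates and OTE uptake, which are not given;
- that every entrant is off drug for only 1 to 15 days: although the synopsis uses that range for the off-treatment period, Section 5.1.4 counts it from the Week 26 visit;
- that main-study conclusions are at risk: the primary and main-study analyses do not use these groups, and the later OTE window contains no placebo time.

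The exposure counts assume that scheduled treatment is taken in full.

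**What to change.** In Section 10.4.4 or the SAP:

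1. Split the 10 mg OTE group by main-study treatment: 10 mg in the OTE after active treatment, and 10 mg in the OTE after placebo. Use individual listings where either group is very small.
2. As a wording clarification, state that the 30 mg and 60 mg continuation groups exclude participants who start the OTE on 10 mg, so that the six groups do not overlap.

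This costs one or two sentences and one more table column in each cohort, using treatment assignments and dose reductions already recorded. Dosing and conduct do not change. The drawback is two small, descriptive, non-randomized 10 mg groups that are still not fully comparable with the other columns, and the text should say so.
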